4.10.3.2. Flu-like Reactions

Flu-like reactions are defined as adverse events with PTs including either (A) Influenza like illness or (B) Pyrexia or Feeling hot or Body temperature increased, plus at least 2 of the following symptoms with the PTs: Chills, Myalgia, or Arthralgia, starting on day of injection or the next day.

Flu-like reactions will also be summarized using the MedDRA coding system, by PT and by treatment group.

Percentage of injections leading to flu-like reactions will be summarized by treatment group using the descriptive statistics.

Percentage of the injections leading to flu-like reactions will be calculated as follows for each patient: $(A/B) \times 100$, where A = number of injections leading to flu-like reactions, and B = total number of injections.

Flu-like reactions will also be listed.

4.10.3.3. Bleeding Adverse Events

Bleeding AEs will be identified based on the Haemorrhages (SMQ) Export from MedDRA and summarized by MedDRA SOC and PT and by treatment group. A by-patient listing will be provided.

4.10.4. Clinical Laboratory Evaluation

The following is the list of lab analytes that will be collected throughout the study:

- Chemistry: sodium, potassium, chloride, bicarbonate, total protein, albumin, calcium, magnesium, phosphorus, glucose, BUN, creatinine, cholesterol, uric acid, total bilirubin, direct (conjugated) bilirubin, indirect (unconjugated) bilirubin, alanine aminotransferase (ALT), aspartate aminotransferase (AST), alkaline phosphatase (ALP), creatinine kinase, gamma-glutamyl transferase (GGT)
- Hematology: red blood cells, hemoglobin (Hb), hematocrit, platelets, mean corpuscular volume (MCV), mean corpuscular hemoglobin (MCH), mean corpuscular hemoglobin concentration (MCHC), white blood cells (WBC), and WBC differential (percentage and absolute count) (basophils, eosinophils, lymphocytes, monocytes and neutrophils)
- Coagulation: activated partial thromboplastin time (aPTT) (sec), prothrombin time (sec), international normalized ratio (INR), D-dimer

TP-GDO-WW-016-08 CONFIDENTIAL Project Document Version No. 2.0
Effective Date: 26 Nov 19 Project Document Effective Date: 13 Dec 2023
Related to: SOP-GDO-WW-019 Page 41 of 61

- Complement: Complement Factor 5a (C5a). (At screening, Complement factor 4 (C4), C1-inhibitor (C1-INH) level and function, Complement 1q (C1q) will be collected.)
- Inflammatory: C-reactive protein (CRP) measured by high sensitivity assay (Hs-CRP)
- Screening tests: hepatitis B surface antigen, hepatitis C antibody, human immunodeficiency virus (HIV) antibody, follicle-stimulating hormone (FSH) (women only, if applicable), and serum beta-subunit of human chorionic gonadotropin (βhCG) (women only). The data will be displayed in by-patient listings.
- Urinalysis (other): color, appearance, specific gravity, pH, P/C ratio, protein, blood, ketones, urobilinogen, glucose, bilirubin, leukocyte esterase, nitrate, microscopic examination. The data will be displayed in by-patient listings.

Missing WBC differential absolute counts and percentages will be derived:

• If WBC differential absolute counts are missing, and percentages are available, then absolute counts will be calculated by multiplying the percentage by total WBC count. Conversely, if absolute count is available, and percentage is missing, then percentage will be calculated by dividing absolute count by the total WBC count. If WBC differential absolute counts are missing, and manual count values are available, then manual count values will be used. If neutrophils count and percentages are missing, and segmented neutrophil and band neutrophil results are available, then neutrophils will be calculated by adding segmented neutrophils and band neutrophils, if only segmented neutrophil result is available, then neutrophils will be set to segmented neutrophils result.

All lab data will be displayed in by-patient listings.

Chemistry, hematology, coagulation, and complement, (result, change and percent change from baseline) will be summarized using descriptive statistics (n, mean, median, standard error, standard deviation, 25th percentile, 75th percentile, minimum, and maximum) by treatment group and analysis visit. Only central lab data will be summarized in by-visit summary. Both central and local lab data will be used in the abnormal summaries described below.

For ALT and AST, the number and percent of patients falling in each of the following categories based on the confirmed results (both central and local lab data will be used) will be tabulated by treatment group:

- ALT or AST $> 3 \times$ upper limit of normal (ULN), which is confirmed
- ALT or AST > $3 \times ULN$ (or the greater of $2 \times baseline value or <math>3 \times ULN$ if the baseline value was > ULN), which is confirmed
- ALT or AST > $3 \times ULN$ (or the greater of $2 \times baseline value or <math>3 \times ULN$ if the baseline value was > ULN), which is confirmed

and

TP-GDO-WW-016-08 CONFIDENTIAL Project Document Version No. 2.0
Effective Date: 26 Nov 19 Project Document Effective Date: 13 Dec 2023
Related to: SOP-GDO-WW-019 Page 42 of 61

total bilirubin $> 1.5 \times ULN$ or INR > 1.5, where "and" required to be based on the same sample

- ALT or AST $> 5 \times$ ULN, which is confirmed
- ALT or AST > 5 × ULN, which is confirmed and persists for ≥ 2 weeks
- ALT or AST $> 8 \times ULN$, which is confirmed

For platelet (K/mm³), the number and percentage of patients falling in each of the following categories based on the confirmed results (both central and local lab data will be used) will be tabulated by treatment group for ≥ 125 , ≥ 100 to < 125, ≥ 75 to ≤ 100 , ≥ 50 to < 75, ≥ 25 to < 50, < 25.

A confirmed value is based on a consecutive lab value within 7 days. If that value is in the same or worse category the initial value is confirmed. If the consecutive value is in a better category, then the initial value is confirmed using the consecutive value category. If there is no retest within 7 days, then the initial value is presumed confirmed. If there are multiple results on the same day, no matter from the same lab vendor or different lab vendors, then the worst value will be utilized in the analysis.

Laboratory data will be presented in by-patient listings.

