1.2.3. Safety Endpoints

The safety and tolerability of ISIS 721744 will be assessed by determining the number, type, severity, and dose-relationship of AEs; vital signs; electrocardiogram (ECG); and clinical laboratory parameters. Safety results in patients dosed with ISIS 721744 will be compared to safety results in patients dosed with placebo.

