8.5.2. Safety Monitoring Rules for Renal Function Test Results

While on treatment, all patients will have renal function tests monitored every 4 weeks during the Treatment and Follow-up Periods as per visit schedule in Appendix A.

In the event of appearance of symptoms or signs consistent with renal dysfunction such as hematuria, polyuria, anuria, flank pain, new-onset hypertension, nausea and/or anorexia, renal function should be tested as soon as possible (ideally within 3 days). Testing at a lab that is local to the patient is permissible for this purpose.

If a patient's results meet criteria 1 or 2 below, the Investigator or designee should confirm the results and initiate weekly monitoring if confirmed. If the event a persistent elevation is observed over 2 consecutive weeks, then refer to Stopping Rules for Renal Function Test Results in Section 8.6.2.

- 1. Serum creatinine increase that fulfills all of the following: \geq 0.3 mg/dL (26.5 μ mol/L) and \geq 40% above baseline creatinine values and > ULN (refer to definition of Baseline in Section Stopping Rules Section 8.6)
- 2. Proteinuria, urine protein/creatinine ratio (UPCR) > 750 mg/g for baseline values ≥ 200 mg/g, or 4 × baseline value for baseline values < 200 mg/g that are confirmed by repeated urine protein/creatinine ratio or by a quantitative total urine protein measurement of > 1.0 g/24 hours

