8.6.2. Temporary Stopping Rules for Renal Function Test Results

In the event of a persistent elevation that is observed over 2 consecutive weeks, for either of the 2 criteria below, dosing of a patient with Study Drug (ISIS 721744 or placebo) may be stopped temporarily:

- Serum creatinine increase that fulfills all of the following criteria: ≥ 0.3 mg/dL (26.5 μmol/L) and ≥ 40% above baseline creatinine values and > ULN (refer to definition of Baseline in Section 8.6)
- 2. UPCR >1000 mg/g, confirmed by a quantitative total urine protein measurement of > 1.0 g/24 hours

The possible dosing re-initiation or follow-up schedule for any events meeting either of these criteria will be determined by the Investigator or designee **in consultation with** the Sponsor Medical Monitor or designee.

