10.6.2. Safety Analysis

The safety and tolerability of ISIS 721744 will be assessed by determining the number, type, severity, and dose-relationship of AEs; vital signs; ECGs; and clinical laboratory parameters. Safety results in patients dosed with ISIS 721744 will be compared to safety results in patients dosed with placebo.

Treatment duration and amount of Study Drug (ISIS 721744 or placebo) received will be summarized by treatment group. Patient incidence rates of all adverse events will be tabulated by Medical Dictionary for Regulatory Activities (MedDRA) system organ class, and by MedDRA term. Tables and/or narratives of treatment emergent deaths, serious and significant adverse events, including early withdrawals due to adverse events, will also be provided.

All treatment emergent AEs, all treatment emergent AEs potentially related to Study Drug, all treatment emergent serious AEs, and all treatment emergent serious AEs potentially related to Study Drug (ISIS 721744 or placebo) will be summarized.

Protocol

Laboratory tests to ensure patient safety including chemistry panel, complete blood count with differential, coagulation panel, complement etc., will be summarized by study visits for each treatment group. These safety variables will also be presented as change and percent change from Baseline over time after Study Drug (ISIS 721744 or placebo) administration, as appropriate.

Vital sign and ECG measures will be tabulated by treatment group. In addition, the number of patients who experience abnormalities in clinical laboratory evaluations will be summarized by treatment group.

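### SAP 4.10.4 leaves the urine protein/creatinine ratio in patient listings only, so the plan produces no by-arm result for the measure behind the protocol's proteinuria rules

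*Combined protocol and SAP*

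**What the plan says.** **Protocol.** Section 2.5.1 names renal function beside platelets and liver chemistry as something to be monitored under stopping rules. Section 8.5.2 sets two renal monitoring triggers. One is a joint creatinine criterion: a rise of at least 0.3 mg/dL, at least 40% above baseline, and above ULN. The other reads "Proteinuria, urine protein/creatinine ratio (UPCR) > 750 mg/g for baseline values" of 200 mg/g or more, or 4 times baseline if baseline is below 200 mg/g, confirmed by repeat UPCR or by urine protein above 1.0 g/24 h. Under 8.6.2, if the creatinine criterion, or UPCR above 1000 mg/g confirmed by 24-hour protein, persists over 2 consecutive weeks, "dosing of a patient with Study Drug (ISIS 721744 or placebo) may be stopped temporarily". On reporting, 1.2.3 states: "Safety results in patients dosed with ISIS 721744 will be compared to safety results in patients dosed with placebo". Section 10.6.2 adds that "the number of patients who experience abnormalities in clinical laboratory evaluations will be summarized by treatment group".

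**SAP 4.10.4.** The urinalysis entry, which contains the P/C ratio, ends: "P/C ratio, protein, blood, ketones, urobilinogen, glucose, bilirubin, leukocyte esterase, nitrate, microscopic examination. The data will be displayed in by-patient listings". The by-arm, by-visit output is defined as: "Chemistry, hematology, coagulation, and complement, (result, change and percent change from baseline) will be summarized using descriptive statistics". Threshold counts follow for liver ("For ALT and AST, the number and percent of patients falling in each of the following categories") and for platelet bands. For confirmation, "If there is no retest within 7 days, then the initial value is presumed confirmed". No renal category appears. SAP 4.2.2 nevertheless includes urinalysis in its baseline definition.

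**The concern.** The protocol has numeric rules for three laboratory risks, and the SAP tabulates threshold counts by arm for two of them. For UPCR it specifies neither a count nor a descriptive summary, so the urinalysis baseline in SAP 4.2.2 feeds no UPCR table.

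At stake is whether a drug-placebo difference in proteinuria short of a dosing change would be visible in the planned outputs. A reader would have to extract it from listings, comparing each value with that patient's own threshold.

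**Working it through.** The plan states no figure to reproduce. The check sets the protocol's renal rules against the SAP outputs, then sizes what falls between them.

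**1. By-arm threshold categories in SAP 4.10.4.** ALT/AST: 6. Platelets: 6. Creatinine or UPCR: 0.

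**2. Creatinine.** It is in the chemistry panel, so result, change and percent change are summarised by arm and visit, with maxima. The joint criterion needs both a change of at least 0.3 mg/dL and at least 40%. If either maximum at a visit falls short, no summarised value at that visit can meet it. What remains open is the count when both maxima are exceeded, and local or unscheduled values outside the by-visit summary, which uses central data only.

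**3. UPCR.** It is in the Appendix B urinalysis panel. The Appendix A urinalysis row has 11 visits: screening; Weeks 1, 5, 9, 13, 17, 21 and 25; post-treatment Weeks 4, 8 and 13. Six fall on treatment after the first dose. With the planned 42, 21 and 21 patients:
- 42 x 6 = 252, 21 x 6 = 126 and 21 x 6 = 126
- total 84 x 6 = 504 values available only in listings

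This is the length of the listing, not an effect size.

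**4. Do other by-arm tables catch these patients?**
- *Adverse events.* Protocol 9.3.1 makes a laboratory deterioration an AE if it brings symptoms or changes treatment. Section 9.5.1 says abnormalities judged not clinically significant should not be reported as AEs.
- *Disposition (SAP 4.4.1).* This counts treatment termination. An 8.5.2 trigger leads to confirmation and weekly monitoring, not termination. For 8.6 rules, protocol 8.5 and 8.8 require permanent discontinuation, which the table would show, but 8.6.2 itself allows a temporary stop and only says that it may happen.
- *SAP 4.12.3.* Kidney tests may be stratified by anti-drug antibody status. This is optional and is not a count against the criteria.

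What is left is mainly a confirmed 8.5.2 UPCR trigger with no symptoms, no dosing change and a not-clinically-significant judgement, plus any 8.6.2 case in which dosing continued.

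**5. The UPCR range between the two rules** (baselines assumed; trigger = 4 x baseline below 200 mg/g, otherwise 750 mg/g):

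| Baseline (mg/g) | 8.5.2 trigger (mg/g) | 8.6.2 limit (mg/g) |
|---|---|---|
| 50 | 4 x 50 = 200 | 1000 |
| 100 | 4 x 100 = 400 | 1000 |
| 150 | 4 x 150 = 600 | 1000 |
| 200 or more | 750 | 1000 |

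**6. Why confirmation matters.** In a simulation, values were independent and lognormal with no true change, baseline was the mean of 2 values, there were 6 visits, and each trigger had one repeat. All 42 patients were taken to have a baseline below 200 mg/g, so that the 4 x rule applies. The within-patient CVs are assumptions; the documents give none.

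| CV | P(any trigger) | x 42 | P(confirmed) | x 42 |
|---|---|---|---|---|
| 30% | 0.0003 | 0.01 | 0.0000 | 0.00 |
| 50% | 0.036 | 1.5 | 0.002 | 0.08 |
| 70% | 0.136 | 5.7 | 0.018 | 0.8 |

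Unconfirmed counts could be largely noise; confirmed counts much less so.

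**7. What a zero count would show.** One-sided 95% upper bounds: 1 - 0.05^(1/42) = 6.9% for 0/42, and 1 - 0.05^(1/21) = 13.3% for 0/21.

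**The case against.** The liver and platelet rules carry more weight. Liver criteria require permanent stopping and are adapted from FDA guidance. Platelet bands include permanent discontinuation, and severe reductions are events of special interest. The renal rule is headed as temporary, there is no renal event of special interest, and 2.5.1 reports no renal signal in earlier studies. Every laboratory value is still listed, and the counts would be small. All of this stands: equal treatment of the three risks is not required, and the point is minor. It does not explain why a ratio measured at every visit has no by-arm summary at all.

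Three stronger readings are tempting and not supported:
- *That the SAP breaches protocol 10.6.2.* That section's by-visit list does not name urinalysis, and its sentence on abnormality counts names no analyte or threshold. The SAP falls short of a general commitment, not a specific renal one.
- *That renal safety as a whole goes unreported by arm.* Creatinine and BUN are in the chemistry panel and are summarised.
- *That patients are less protected, or that a renal signal is concealed.* Alerts, weekly monitoring after a confirmed trigger and DSMB review are unaffected, and nothing in the documents shows such a signal.

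The simulation rests on assumed CVs and says nothing about how often rises occur. It bears only on how the table should be built.

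**Conclusion.** The point holds for UPCR: the listing-only rule is explicit, and following it gives no by-arm result. For creatinine only the joint-criterion count is missing. This is a minor gap, confined to safety reporting, with no effect on efficacy, power, type I error or patient monitoring.

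The description of who is missed assumes that AE and discontinuation reporting work as 8.5, 8.8, 9.3.1 and 9.5.1 require. How many such patients there would be cannot be derived from the documents. Any resulting counts are descriptive only, given the upper bounds above.

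**What to change.** Keep the listings and add to SAP 4.10.4:

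1. A by-visit UPCR summary by treatment group: result and change from the SAP 4.2.2 baseline.
2. A descriptive by-arm n (%) table, with no test, using central and local, scheduled and unscheduled values, of patients with:
   - (a) UPCR meeting 8.5.2 (above 750 mg/g if baseline is 200 mg/g or more; 4 x baseline if below 200 mg/g), confirmed by repeat UPCR or by urine protein above 1.0 g/24 h;
   - (b) UPCR above 1000 mg/g, in two rows: those meeting 8.6.2 in full (24-hour protein above 1.0 g and persistence over 2 consecutive weeks), and those confirmed by repeat UPCR only;
   - (c) creatinine at least 0.3 mg/dL and at least 40% above baseline and above ULN, all in the same sample.

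Show values with no retest in a separate unconfirmed row, and state that this departs from the presumed-confirmed rule used for liver and platelets; step 6 gives the reason. Flag patients already above a UPCR threshold at baseline, so that they are not counted as new rises; protocol 5.2 sets no UPCR exclusion.

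Unscheduled retests are needed because scheduled visits are 4 weeks apart. The 24-hour protein can be used only where it was collected, since it is not in Appendix B or the SAP analyte list. No extra visits or samples are required. After database lock, SAP section 1 allows the additions through an addendum or the study report. The cost is minor programming; the drawback is small, noisy counts.

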8.5.1. Safety Monitoring Rules for Liver Chemistry Tests

The following rules are adapted from the draft guidance for industry, "Drug-Induced Liver Injury: Premarketing Clinical Evaluation," issued by the U.S. Department of Health and Human Services, Food and Drug Administration, July 2009. For a definition of Baseline please refer to guidance in Section 8.5 above.

All patients will have liver chemistry tests monitored every 4 weeks during the Treatment Period. Upon completion of the study Treatment Period, liver chemistry tests should be monitored as per visit schedule in Appendix A.

In the event of appearance of symptoms or signs of hepatic injury (jaundice, fatigue, nausea, vomiting, right upper quadrant pain or tenderness, fever, rash, abnormal bleeding or bruising, or eosinophilia > ULN) liver enzymes and bilirubin should be tested as soon as possible (ideally within 3 days). Testing at a lab that is local to the patient is permissible for this purpose.

In the event of an ALT or AST measurement that is $> 3 \times \text{ULN}$ (or the greater of $2 \times \text{baseline}$ value or $3 \times \text{ULN}$ if the baseline value was > ULN) at any time during the study (Treatment or Post-Treatment Period), the initial measurement(s) should be confirmed as described above. Additional confirmatory measurements should also be performed if ALT or AST levels increase to $5 \times \text{ULN}$.

Frequency of Repeat Measurements: Patients with confirmed ALT or AST levels $> 3 \times \text{ULN}$ (or the greater of 2 × baseline value or 3 x ULN if the baseline value was > ULN) should have their liver chemistry tests (ALT, AST, Alkaline Phosphatase (ALP), international normalized ratio [INR], and total bilirubin) retested at least once-weekly until ALT and AST levels become $\le 1.2 \times \text{ULN}$ or $1.2 \times \text{baseline}$ value if the baseline value was > ULN].

Further Investigation into Liver Chemistry Elevations: For patients with confirmed ALT or AST levels $> 3 \times \text{ULN}$ (or the greater of $2 \times \text{baseline}$ value or $3 \times \text{ULN}$ if the baseline value was > ULN), the following evaluations should be performed:

- 1. Obtain a more detailed history of symptoms and prior and concurrent diseases
- 2. Obtain further history for concomitant drug use (including nonprescription medications, herbal and dietary supplement preparations), alcohol use, recreational drug use, and special diets

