8.6.1. Stopping Rules for Liver Chemistry Elevations

In the event of laboratory results meeting the following criteria, and the event is without an alternative explanation as discussed with the Sponsor Medical Monitor, dosing of a patient with Study Drug (ISIS 721744 or placebo) will be stopped permanently; values that are not confirmed due to failure to retest or missing lab values will be presumed confirmed:

- 1. ALT or AST $> 8 \times ULN$, which is confirmed
- 2. ALT or AST > $5 \times ULN$, which is confirmed and persists for ≥ 2 weeks
- 3. ALT or AST > $3 \times ULN$ (or the greater of 2 x baseline value or $3 \times ULN$ if the baseline value was > ULN), which is confirmed **and** total bilirubin > $1.5 \times ULN$ or INR > 1.5
- 4. ALT or AST > 3 × ULN (or the greater of 2 x baseline value or 3 x ULN if the baseline value was > ULN), which is confirmed, **and** the new appearance (i.e., onset coincides with the changes in hepatic enzymes) of fatigue, nausea, vomiting, right upper quadrant pain or tenderness, fever, rash, and/or concomitant eosinophilia (> ULN)

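### The SAP's combined ALT/AST plus bilirubin/INR row requires both abnormalities in one sample, a condition protocol 8.6.1(3) does not state, so a case split across draws can be missing from that row

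*Combined protocol and SAP*

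**What the plan says.** **Stopping rule (Protocol 8.6.1).** When a listed criterion is met, "dosing of a patient with Study Drug (ISIS 721744 or placebo) will be stopped permanently", provided that "the event is without an alternative explanation as discussed with the Sponsor Medical Monitor". Criterion 3 joins a confirmed ALT/AST elevation (>3 x ULN, or the greater of 2 x baseline and 3 x ULN if baseline exceeded ULN) to total bilirubin >1.5 x ULN or INR >1.5. The joining words are "which is confirmed and total bilirubin >". Nothing is said about whether the two abnormalities must come from one draw.

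**Follow-up testing (Protocol 8.5.1).** After a confirmed elevation, five tests (ALT, AST, ALP, INR and total bilirubin) are "retested at least once-weekly until ALT and AST levels become" no more than 1.2 x ULN, or 1.2 x baseline if baseline exceeded ULN.

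**Table (SAP 4.10.4).** By treatment group, the SAP gives "the number and percent of patients falling in each of the following categories based on the confirmed results", using central and local results. There are six categories:

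- confirmed ALT/AST >3 x ULN;
- confirmed ALT/AST above 3 x ULN or the baseline-adjusted limit;
- that second category plus total bilirubin >1.5 x ULN or INR >1.5, with the pairing "required to be based on the same sample";
- confirmed ALT/AST >5 x ULN;
- confirmed ALT/AST >5 x ULN lasting at least 2 weeks;
- confirmed ALT/AST >8 x ULN.

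The SAP does not define what counts as one sample. All laboratory data are also listed by patient.

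**The concern.** The rows for >8 x ULN, and for >5 x ULN lasting 2 weeks, carry protocol criteria 1 and 2 over without any added condition. The combined row carries criterion 3 over and narrows it. SAP 4.16, which sets out changes from the planned analysis, does not mention the narrowing.

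The condition matters because of the order in which results can arrive. The protocol goes on measuring bilirubin and INR while the enzymes are falling. If bilirubin or INR crosses its limit after ALT/AST are back under 3 x ULN, no single draw holds both abnormalities.

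At stake is the only by-arm count of combined hepatic abnormality that the SAP defines. Liver chemistry is one of the laboratory risks for which the protocol sets monitoring and stopping rules (Protocol 2.5.1). The ALT/AST-only rows cannot separate an isolated enzyme rise from a combined one, and listings give no count by arm.

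**Working it through.** The plan gives no figure to reproduce here. The check sets the two definitions side by side and runs result patterns through both.

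**1. The definitions**

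| Element | Protocol 8.6.1(3) | SAP 4.10.4 combined row |
|---|---|---|
| ALT/AST | confirmed, >3 x ULN or baseline-adjusted limit | same |
| Bilirubin / INR | >1.5 x ULN / >1.5 | same |
| Timing link | none stated | same sample |
| Alternative explanation | must be absent | not considered |

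**2. A single case.** All values are assumed: baseline ALT at or below ULN, INR normal, no alternative explanation.

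| Draw | ALT (x ULN) | Bilirubin (x ULN) | Both above limit? |
|---|---|---|---|
| Day 0 | 4.0 | 1.2 | No: 1.2 < 1.5 |
| Day 3 | 3.5 | 1.4 | No: 1.4 < 1.5 |
| Day 10 | 2.8 | 1.8 | No: 2.8 < 3 |

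- Confirmation: the day 3 value meets the protocol's 3-day target for a repeat specimen (8.5) and the SAP's 7-day rule, and 3.5 is still above 3.
- Retesting is still required on day 10, because 2.8 > 1.2.
- Criterion 3, read as allowing separate draws, is met on day 10: ALT is confirmed and bilirubin is 1.8 > 1.5.
- SAP rows: confirmed ALT/AST >3 x ULN = 1; baseline-adjusted row = 1; combined row = 0.
- With 42 patients planned on the every-4-week regimen, 1/42 = 2.4% becomes 0/42 = 0% in the combined row.

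**3. Which patterns are affected.** Take three consecutive draws with ALT/AST at 1, 2 or 4 x ULN, bilirubin at 1 or 2 x ULN, INR normal, baseline at or below ULN, and confirmation by the next draw.

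- All patterns: 3^3 x 2^3 = 27 x 8 = 216.
- Confirmed ALT/AST needs two adjacent values of 4: three patterns (4,4,x) plus three (x,4,4), less (4,4,4) counted twice, gives 5.
- Bilirubin raised on at least one draw: 2^3 - 1 = 7.
- Patterns meeting criterion 3 as written: 5 x 7 = 35.
- Of these, patterns with no draw showing both: 4. In two, bilirubin is raised only after the enzymes fall: ALT (4,4,1) or (4,4,2) with bilirubin (1,1,2). In two, it is raised only before they rise: ALT (1,4,4) or (2,4,4) with bilirubin (2,1,1).
- All 35 are counted in the confirmed ALT/AST >3 x ULN row.

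These are counts of patterns, not probabilities. With only two draws there is no gap: confirmation then requires both ALT values to be above 3, so any raised bilirubin shares a draw with one of them. The gap needs at least a third draw, and 8.5.1 supplies it.

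**The case against.** **Silence is not contradiction.** Criterion 3 neither requires one sample nor says that separate draws may be combined. The SAP may only be giving its table a reproducible definition, and it does not claim to count actual stops. This stands in part: a reader might infer that the SAP contradicts the protocol, but the documents do not settle how criterion 3 is read across draws. Two points favour the wider reading. Criterion 4 in the same list does tie symptoms in time to the enzyme changes, while criterion 3 has no such link. And 8.5.1 follows bilirubin and INR past the enzyme peak.

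**The patient remains visible.** A reader might infer that a stopped patient disappears from the liver table. That is not so. Criterion 3 presupposes the confirmed ALT/AST elevation, which has its own rows. Treatment terminations are tabulated by major reason (SAP 4.4.1), adverse events leading to drug discontinuation are listed (SAP 4.10.2), and Protocol 10.6.2 provides tables or narratives for early withdrawals due to adverse events. This stands in full, and confines the point to one row.

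**The INR part is workable.** INR sits in the coagulation panel ("prothrombin time (sec), international normalized ratio (INR), D-dimer") and ALT/AST in chemistry, so a reader might infer that one sample can hardly ever hold both. That follows only if a sample means a single tube. Appendix A footnote 11 groups chemistry and coagulation at the same visits, and 8.5.1 names INR and ALT/AST in one retest set. One collection is the sensible reading; what remains is that the term is undefined.

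**Numbers alone do not make a stop.** The stop also depends on there being no alternative explanation, so no purely numerical row can equal the patients stopped. This stands, and is why a separate flag is needed.

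**A wider window admits noise.** Protocol 5.2 allows patients with Gilbert's syndrome whose total bilirubin is up to 5 mg/dL, so unrelated bilirubin rises could be paired with an enzyme rise. This stands as a reason to add a row instead of replacing the existing one.

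**Conclusion.** The point holds for the combined row only. SAP 4.10.4 attaches a same-sample condition that Protocol 8.6.1(3) does not state, and a case whose bilirubin or INR crosses the limit on a later retest can be missing from that row. The patient is still counted in the two ALT/AST-only rows and shown in the listings.

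The size is at most the number of such patients, one count each: in the example, 0% instead of 2.4% in the planned every-4-week group. It would be tempting to call this the difference between a signal and none. The documents give no frequency for split-draw cases, and the same patient shows in two neighbouring rows, so that claim is not supported.

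The conclusion assumes that criterion 3 can be met on separate draws, that the enzyme elevation is confirmed under both documents, and, for an actual stop, that no alternative explanation was found. It takes no position on which clinical rule is right.

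**What to change.** In SAP 4.10.4:

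1. Keep the existing combined row and define the same-sample condition as the same collection date.
2. Add a by-arm row for patients who meet the confirmed ALT/AST criterion and have total bilirubin >1.5 x ULN or INR >1.5 on any central or local sample from the first elevated ALT/AST until the 8.5.1 resolution level. State the start explicitly. If it is the first value above the ALT/AST limit, the two late patterns above are captured and the two early ones are not.
3. Flag patients actually stopped under 8.6.1(3), since neither numerical row can stand in for them.
4. Reconcile the SAP and protocol passages on whether the abnormalities may come from separate draws, leaving the clinical stopping rule unchanged.

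The cost is SAP wording and one additional table derivation from laboratory data already collected. Protocol 8.8 already requires the reason for discontinuation to be recorded; the documents do not say whether it names the criterion, so the flag may need a check of source records. After database lock, SAP section 1 allows the change to be described in an addendum or the study report. The drawback is that some coincidental bilirubin elevations, for example in Gilbert's syndrome, will enter the new row and need a footnote or narrative.
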